7.2.2.4 Additional visits

Between V2 and V3, additional dressing changes can be performed as often as necessary according to the instruction for use of the investigational product assigned. Lomatuell Pro® and UrgoTul® may be left in place up to 7 days. In this case, the data collected during these "in-between" visits will be collected in the Nurse Diary.

Data collected during these visits are:

- Number of the additional visit
- Date of the visit
- Reason for dressing change

- Presence of complete re-epithelialization (NB! In case of complete epithelialization all procedures, required for Visit 3 should be performed, data is to be recorded in the CRF section Visit 3 and not as an additional visit)
- Appearance of the dressing before removal
- Bleeding during dressing removal
- Appearance of the wound bed (bleeding, maceration, inflammation, infection, and tissue in-growth in the dressing holes)
- Appearance of the surrounding skin (inflammatory signs, irritation, allergic rash/eczema, blistering, skin stripping, maceration, dry, trauma to wound edges, product degradation on the skin, hematoma)
- Amount of exudate
- Wound moisture
- Local treatment
- Number of dressings used
- Application of dressing
- Secondary dressing
- Initials of person in charge for dressing change

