7.8.2.2 Secondary Objectives

Variables

Secondary efficacy criteria will be as follows:

- Complete healing at V3 (D21+2 or earlier, as soon as the wound is epithelialized completely).
- Wound condition assessment at V2 and V3 or ET
- Surrounding skin condition assessment at V2 and V3 or ET
- Global assessment of the dressing by the investigator at V2 and V3 or ET
- Global assessment of exudate management (efficiency of the CL to drain exudates to the secondary dressing)
- Global assessment of the dressing by the subject at V3 or ET
- Assessments from study nurse's booklet (at each dressing change)
- Adverse events (AEs), serious adverse events (SAEs), device effects (ADEs), serious device effects (SDEs), device deficiencies (DDs), occurring during the investigation

Measurements

Complete healing at V3

The evaluation of complete healing status (100% of epithelialization (first epithelia layer) of the wound) will be performed by the investigator at V3 (D21 \pm 2 or earlier if the wound is

healed before D21), as the phenomenon of epithelialization is visible to the naked eye). Data on complete healing will be reported in the CRF.

In addition to the evaluation of complete healing status performed by the investigator at V3, a blind assessment of healing will be performed by an independent assessor - chosen prior to the start of investigation - on photographs taken by investigators at V1 and at the final visit (V3). All photographs will be taken of the wound site and adjacent intact skin under standardized conditions (see Appendix 17.2). The digital photographs will be captured and available to the independent assessor chosen. A blind assessment of these photographs will be performed using W.H.A.T. in order to evaluate the healing status.

Wound condition assessment

Bleeding of the wound bed

The investigator will have to report the possible occurrence and intensity of bleeding at each dressing removal (including V1).

Maceration of the wound

Maceration refers to the skin changes seen when moisture is trapped against the skin for a prolonged period. The investigator will evaluate this parameter at each dressing removal (including V1).

Inflammation

The investigator will evaluate the presence of inflammation at the V1 and at each dressing removal.

• Infection

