7.9.1.2 Efficacy analyses

Analysis of the main criterion

The test for the non-inferiority of Lomatuell Pro® vs UrgoTul® for the main criterion will be carried out through a confidence interval (CI) approach. Non-inferiority will be established if the lower unilateral limit of the 97.5% CI in the PP population for the between-treatment difference (Lomatuell Pro® - UrgoTul®) in the percentage of wound dressing associated with a pain < 30 mm on VAS at V2 does not exceed -10%.

Considering that the studied population is "patients with an acute wound" and that the primary endpoint will be assessed at V2 (Day 3±2); we can expect very few drop-outs. We also expect few patients with a major protocol deviation. Therefore, we can conclude that an assumption of 10% attrition rate is acceptable for this study.

In order to unambiguously conclude to non-inferiority in agreement with most of guidelines, the same analysis will be performed on the mITT population. In case of missing data to evaluate the primary criterion, the subjects will be considered as failures. The trial will be considered positive if both approaches support noninferiority.

Adjustment

The frequency of analgesic intake will also be analysed. In case of a significant difference between the 2 dressing groups, the analysis of the primary criterion (painless dressing removals) will be adjusted using a Mantel-Haenszel test.

Analysis of the secondary criteria

The following statistical tests will be used to analyse the secondary criteria according to the criteria type:

- Qualitative nominal criteria will be compared using a Chi² test.
- Qualitative ordinal criteria will be compared using a Mann-Whitney-Wilcoxon test
- Quantitative criteria will be compared using an analysis of variance (ANOVA)

Degree of significance

The criteria for which the degree of significance of the bilateral test will not exceed 0.05 (statistically significant difference) will highlight the specificities between the 2 groups of dressing.

Percentage of complete healing at V3

A wound will be considered as completely healed when there is 100% of epithelialization (first epithelia layer) of the wound. The percentage of wounds healed will be calculated based on a blind assessment from photographs using W.H.A.T.

Assessment of the wound condition

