For the other parameters (appearance of the dressing before removal, bleeding of the wound, condition of the wound, cleaning is required on or around the wound and type of solution used), the statistical unit is not the patient but the dressing change. The percentage of each modality of the other parameters will be calculated.

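### Nurse-booklet outcomes take the dressing change as the unit, so the protocol's general rule for secondary criteria puts Chi² and rank tests on repeated observations from the same patient

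*Protocol*

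**What the plan says.** Protocol section 7.8.2.2 includes among the secondary efficacy criteria "Assessments from study nurse's booklet (at each dressing change"). Section 7.9.1.2 opens its part on secondary criteria with a general rule: "The following statistical tests will be used to analyse the secondary criteria according to the criteria type". For nominal items, "Qualitative nominal criteria will be compared using a Chi² test"; for ordinal items, "Qualitative ordinal criteria will be compared using a Mann-Whitney-Wilcoxon test". The threshold follows: "The criteria for which the degree of significance of the bilateral test will not exceed 0.05" are to be read as showing how the two dressings differ.

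Later in the same section, the booklet paragraph handles the total and mean number of changes separately. For the remaining booklet parameters it states that "the statistical unit is not the patient but the dressing change", and then: "The percentage of each modality of the other parameters will be calculated".

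Section 7.2.2.4 sets no limit on the number of booklet entries per patient: "Between V2 and V3, additional dressing changes can be performed as often as necessary". Sections 7.4.1 and 7.4.2 give a usual wear time of 2 to 4 days, up to 7, for both dressings. Section 7.9.3 randomises patients 1:1.

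The protocol names no GEE, mixed model, cluster-robust variance or patient-level summary. The SAP supplied is written for another product's protocol (its section 4) and plans no formal comparison (its section 7.2), so it does not settle the matter.

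**The concern.** Chi² and Mann-Whitney-Wilcoxon tests both assume independent observations. Successive changes on one wound share the patient, the wound and the nurse's habits, so their results will tend to resemble one another. Counting each change as a separate observation credits the trial with more information than it has, and the tests reject too often when the dressings do not differ.

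The pooled percentages have a related feature. A patient with 9 changes counts 9/2 = 4.5 times as much as a patient with 2. How often a dressing is changed depends on the condition of the wound and is determined after randomisation, so the weights favour slow or troublesome wounds and may differ between arms.

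At stake is the reading of secondary results on bleeding and dressing appearance in an open-label trial: a nominally significant difference on these items would carry less evidence than its p-value suggests.

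**Working it through.** **1. The plan's own figure.** The booklet analysis has no stated sample size or error calculation. The only figure to reproduce is the primary one in section 7.9.2: 95% in both arms, margin 10%, one-sided 2.5%, power 80%.

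n = (1.960 + 0.842)² × 2 × 0.95 × 0.05 / 0.10² = 74.6, so 75 per arm. With 10% attrition, 75/0.9 = 83.3, so 84. Both reproduce. This endpoint uses one removal per patient at V2, so clustering does not enter.

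**2. Do the tests apply to the booklet items?**
- The booklet assessments are on the list of secondary criteria (7.8.2.2), and the test rule covers the secondary criteria (7.9.1.2).
- The booklet paragraph mentions only percentages. However, 7.9.1.2 uses the same kind of wording for wound condition, surrounding skin and both global assessments. If it meant no test, the general rule would have almost nothing to act on.
- Where description alone is intended, the protocol says so: section 7.9.1.3 does this for safety. Nothing equivalent is written for the booklet.

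**3. Inputs for the size of the effect.** The documents give neither the mean number of changes per patient (m) nor the intraclass correlation (ICC); both are assumptions.
- m = 2 to 9. From D3 to D21 there are 18 days; 18/7 = 2.6 and 18/2 = 9 set the rough limits. The removal at V3 is recorded in the CRF rather than the booklet, and wounds that close early give fewer changes, so 9 is near the top.
- ICC = 0.05 to 0.5.

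**4. Formulas.** Design effect DE = 1 + (m − 1) × ICC. Ratio of naive to correct standard error = 1/√DE. True error of a nominal two-sided 5% test = 2 × [1 − Φ(1.96/√DE)].

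Central case, m = 4 and ICC = 0.2: DE = 1 + 3 × 0.2 = 1.60. The ratio is 1/√1.60 = 0.79. The true error is 2 × [1 − Φ(1.55)] = 12.1%. With 84 patients per arm, 336 changes carry the information of 336/1.60 = 210.

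| m | ICC 0.05 | ICC 0.2 | ICC 0.5 |
|---|---|---|---|
| 2 | 5.6% | 7.4% | 11.0% |
| 4 | 6.8% | 12.1% | 21.5% |
| 6 | 8.0% | 16.6% | 29.5% |
| 9 | 9.8% | 22.4% | 38.1% |

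**5. Check by simulation.** Beta-binomial data, 84 patients per arm, assumed event rate 20%, 20,000 runs per scenario, Chi² on changes:
- m = 4, ICC 0.2: 11.8%.
- m = 9, ICC 0.5: 38.2%.
- Number of changes varying evenly from 1 to 9: 7.8% at ICC 0.05, 17.3% at 0.2, 30.2% at 0.5.
- One observation per patient: 4.8% to 5.4%, as it should be.

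The formula and the simulation agree, and the excess error disappears once each patient contributes one observation.

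**The case against.** The strongest reply is that the booklet paragraph promises percentages and nothing more, and that being on the list of secondary criteria does not prove testing, since adverse events are on the same list and are only described. It stands this far: testing of booklet items follows from the general rule and is not stated in the booklet paragraph. It does not remove the point, because safety has its own descriptive-only clause and the booklet does not. If description was intended, the protocol needs to say so.

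Other parts of the reply are right and set limits:
- A reader might infer that confidence intervals will be too narrow. No interval is planned for these items; the exposure is the tests.
- A reader might take these as the outcomes closest to the adherence question. Section 5 gives that role to pain at removal, the primary endpoint. Bleeding, tissue in-growth and wound adhesion are also recorded at V2 and V3, outside the per-change rule.
- A reader might conclude that the plan will produce false differences. Inflated error raises their chance; it does not make any given difference false.
- Additional visits are optional (section 7.2.1, Table 1) and dressings may stay on for 7 days, so some patients will supply one booklet entry or none. The mild end of the range, about 6% to 11% at 2 changes, is therefore realistic.
- A per-change percentage is a legitimate description of device performance. Weighting by changes is a choice of target quantity that should be made knowingly; it is not an error in itself.

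**Conclusion.** The point holds as a defect in the secondary analysis. Read as written, section 7.9.1.2 applies tests that need independent observations to several changes from the same patient. The direction is certain for any positive within-patient correlation. The size is not: it rests on assumed values of m and ICC, over which the true error of a nominal 5% test runs from about 6% to 38%. The central value of about 12% is an illustration and not an estimate for this trial.

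The documents do not support extending this to the trial's main conclusion. The non-inferiority test and its sample size stand, and no success criterion depends on a booklet item. It should be corrected, but it does not threaten the primary result.

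**What to change.** Amend the booklet paragraph of Protocol section 7.9.1.2, and carry the change into an SAP written for this trial, in one of these ways:

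- **Patient as unit.** Reduce each parameter to one value per patient, either the proportion of changes with the finding or any occurrence, and compare those values between arms. State how patients with no booklet entries are handled. Any occurrence becomes more likely with more changes, so the proportion is the safer default.
- **Change as unit, clustering allowed for.** Use GEE with patient as cluster and robust standard errors.

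Per-change percentages may still be shown under either option, labelled as descriptive and without tests. If no comparison is wanted, that label alone is enough.

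No extra patients or data are needed. The cost is slightly more analysis work and, in general, larger p-values on these secondary items.

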7.9.1.3 Safety analyses

Safety analyses will be descriptive overall and by dressing group. Any local and general adverse events occurring and those already present, but worsening, during the course of the investigation will be described on the safety population. Frequencies will be provided per dressing group and overall describing the type of event: device deficiency (DD), adverse event (AE), serious AE (SAE), adverse device effect (ADE), serious ADE (See Section 11).

7.9.2 Determination of Sample Size

A number of n = 75 subjects per group will allow a 80% power to demonstrate non-inferiority with a type I error of 2.5% one-sided considering 95% of dressing changes with a pain VAS value < 30 mm at D3 and a 10% non-inferiority margin, as recommended by the sponsor. Thus, considering an attrition rate equal to 10%, it is necessary to include n = 84 subjects per group to obtain the required power.

7.9.3 Randomization

Patients will be randomized in a 1:1 ratio to each treatment arm. A randomization list will be generated using a validated pseudo-random number generator, yielding reproducible and non-predictable results. Access to the randomization list will be controlled and documented. The method of permuted blocks will be used. The block size will be documented in the Study Report. Randomization will be centralized and performed by Interactive Web Response System (IWRS) at RCTs. Investigators will receive the result of the randomisation by email.

8 DATA MANAGEMENT

The sponsor provides all necessary technical equipment and documentation to the participating site or investigator, respectively. This includes study Clinical Investigation Plan, study nurses confirmation forms, CRFs, and contact details of the sponsor and monitor.

Data recording is conducted on paper-CRFs, except randomisation which is performed on IWRS.

All completed original CRF forms (as well as the study nurses diary) should be signed by the investigator and forwarded to RCTs within four weeks after completion at the latest. Additionally, pictures of wound will be provided to RCTs on an USB Key.

The data collected on the CRFs will be the data entered by RCTs and used for statistical analysis. Pictures of wound will be provided to RCTs on an USB Key for measurement by W.H.A.T, by Lohmann & Rauscher.

9 STUDY REPORT AND PUBLICATION POLICY

The data resulting from this study will be collected on behalf of Lohmann & Rauscher by RCTs and will be analyzed after all subjects have completed the study, and all data validation checks have been performed. RCTs will conduct the analysis of the clinical data and provide the results in a study report in cooperation with the sponsor. The study report will be submitted to the ethics committees involved.

It is planned to publish the trial results in a scientific journal and at German or international congresses. Publication of the results of the trial as a whole is also intended.

Any published data will observe data protection legislation covering the trial subject and investigators. Success rates or individual findings at individual trial sites are known only to the sponsor. By signing the contract to participate in this trial, the investigator declares that he or she agrees to submission of the results of this trial to national and international authorities for approval and surveillance purposes, and to the Federal Physicians Association, the Association of Statutory Health Fund Physicians and to statutory health fund organizations, if required. At the same time, the investigator agrees that his or her name, address, qualifications and details of his or her involvement in the clinical trial may be made known to these bodies.

The lead authorship of the manuscript of the whole clinical trial results and the co-authorships will be related to the amount of recruited patients. Lohmann & Rauscher staff will be included as co-authors.

The publication or presentation of the results of a single study center requires prior notice and prior comment and approval from the sponsor Lohmann & Rauscher. The support by Lohmann & Rauscher is to be mentioned in any publication. A copy of all publications will be sent to Lohmann & Rauscher.

10 QUALITY ASSURANCE

10.1 Quality assurance

All information about study subjects will be kept confidential. The CRFs will be pseudonymized. The CRFs will not contain any patient details like name, date of birth (only MM/YYYY will be collected), etc.

The CRF is the clinical data collection instrument for this study. All data requested on the CRF must be recorded. Missing data should be explained or filled in retrospectively by the respective investigator.

After data entry in the clinical data base (CDB), each data will be automatically checked and informatics queries may be issued.

These queries will be sent to the site in order to have them resolved in due time. The study nurses will have the help of RCTs within phone calls if necessary.

If any recording error has occurred on the CRF, straight line should be drawn through the incorrect entry and the correct data entered besides. The corrected information must be confirmed through initials and date by the investigator. Errors should not be blurred or erased.

The images gained during the course of the study will be evaluated by a blinded observer to reduce bias.

During the study, the study nurse coordinator will have regular contacts with the investigation site. It is planned to have also audit visits. Data in the CRF will be considered as source document, except for demographics and inclusion/exclusion criteria and randomisation reports. Moreover, the study nurse will have their own nursing record in which the main information regarding the care will be noted (i.e.: name, patient coordinates, date of care, act of care and comment).

It has to be verified the clinical study is conducted according the CIP, and subsequent amendments, and the applicable legal requirements.

All documents associated with the present study are archived for a period of 15 years at the sponsor's site, study nurse site and at study nurse coordinator's site.

10.2 Protocol Deviations

General definition: major protocol deviations are any protocol deviations that might significantly affect the completeness, accuracy, or reliability of the study data or that might significantly affect a subject's rights, safety, or well-being. Relevant major protocol deviations may include errors in treatment assignment, the use of excluded medication, poor compliance, loss to follow-up and missing data (cf. ICH E3. Questions and answers (R1). January 2013 and ICH E9).

In this trial, the following protocol deviations will be considered as major and will therefore lead to exclude patients from the PP set:

- Patient randomized while an inclusion criterion is not met
- Patient randomized while an exclusion criterion is met
- Patient not treated as per protocol between V1 (D0) and V2 (D3±2):
 - Patient randomized to Lomatuell Pro® but actually received UrgoTul® at D0
 - o Patient randomized to UrgoTul® but actually received Lomatuell Pro® at D0
- Pain assessment (VAS) during removal at V2 (D3±2) is missing (i.e. primary endpoint is missing)
- Pain assessment (VAS) during removal at V2 performed out of the time-window (i.e. at D6 or later)

Further major protocol deviations may be defined during the conduct of the trial, if deemed relevant. The list of major protocol deviations will have to be finalized and documented (for example, in the data review minutes) prior to the database lock.

11 SAFETY AND EVENT HANDLING

The following definitions on the basis of DIN EN ISO 14155:2012-01 will be employed:

Adverse event (AE)

Any untoward medical occurrence, unintended disease or injury, or untoward clinical signs (including abnormal laboratory findings) in subjects, users or other persons, whether or not related to the investigational medical device.

Adverse device effect (ADE)

Adverse event related to the use of an investigational medical device.

Serious adverse event (SAE)

Adverse event that

- a) led to death,
- b) led to serious deterioration in the health of the subject, that either resulted in
 - 1) a life-threatening illness or injury, or
 - 2) a permanent impairment of a body structure or a body function, or
 - 3) in-patient or prolonged hospitalization, or
 - 4) medical or surgical intervention to prevent life-threatening illness or injury or permanent impairment to a body structure or a body function,
- c) led to foetal distress, foetal death or a congenital abnormality or birth defect

Serious adverse device effect (SADE)

Adverse device effect that has resulted in any of the consequences characteristic of a serious adverse event.

Device deficiency

Inadequacy of a medical device with respect to its identity, quality, durability, reliability, safety or performance.

Device deficiencies that did not lead to an adverse event but could have led to a medical occurrence

- a) if either suitable action had not been taken,
- b) if intervention had not been made, or
- c) if circumstances had been less fortunate,

shall be handled as specified for SADEs. These events are defined as device deficiencies with SADE potential.

Events that are assessed as SADE or device deficiencies with SADE potential by the investigators might match the definition of a reportable event.

Incidents

Any malfunction or deterioration in the characteristics and/or performance of a device, as well as any inadequacy in the labeling **or** the instructions for use which might lead to or might have led to the death of a patient, or USER or of other persons or to a serious deterioration in their state of health. (Directive 93/24 EEC)

An incident is a malfunction, failure or a modification of the features or performance or an inaccurate label or instruction manual for a medical device, which directly or indirectly caused, may have caused in the past, or may cause in the future, death or a serious aggravation of the state of health of a patient, a user or another person (MPSV § 2 (1)).

All SAEs, SADEs, device deficiencies with SADE potential or incidents according to the European Directive 93/42/EEG and national law have to be immediately reported to Lohmann & Rauscher GmbH & Co.KG, [name] by fax to [contact] or by E-mail to [contact].

Version 2.0 – March 29, 2019

